7.1.6.3. Supplementary Analyses

Supplementary analysis of the primary efficacy endpoint will be performed on the Microbiologically Evaluable (ME) Population with all other details as per Section 7.1.6.1.

In the event that one or more investigators/sites receive a CAPA that stipulates a supplementary analysis should be conducted excluding them as agreed by a multidisciplinary GSK team prior to unblinding, a supplementary analysis will be performed. A flag will be included to identify subjects enrolled by those investigators/sites. This will enable further subpopulations to be defined for the primary analysis population (Micro-ITT). These subpopulations (micro-ITT [CAPA]) may be defined which will consist of all subjects in the micro-ITT population excluding subjects from those investigative sites. The methods described for the primary analysis (Section 7.1.6.1) may then be repeated on the newly defined analysis population(s).

7.1.6.4. Subgroup Analyses

Subgroup analyses will be performed for the microbiological success rate at the TOC visit in Micro ITT and ME population. Microbiological success rate and Exact Clopper-Pearson confidence interval in each treatment group at each level will be calculated. Unadjusted difference in microbiological success rate will be included and summarized with 2-sided 95% CI using MN method (adjustment will not be performed). For each specific subgroup, if there are not enough participants (i.e., <10 participants across treatment groups), treatment difference in microbiological success rate and CI will not be derived. A forest plot showing the results for the subgroup analyses of microbiological success rate will be presented.

See Section 5.4.2 for definition of subgroups.

7.1.6.5. NG Phenotype and Genotype Subgroups

- NG isolated at Baseline will be categorized as listed below. The necessity of these categories will depend on the phenotypes that are recovered. Any present in 10 or more participants across treatment groups will be summarized separately.
- Summaries of participant-level microbiological success, failure, and reasons for failure at the TOC (including phenotypic and genotypic subcategories) overall and by subgroup including by sex and sexual orientation (men who have sex with men [MSM], men who have sex with women [MSW], or female) and age (<18 years, ≥18 to 65 years, or >65 years), geographic region, including country and FDA region) will be presented by phenotypic and genotypic subcategories (Note: FDA region for CLSI summaries only). Phenotypic and genotypic subcategory analysis for subgroups as described above will also be conducted for tables showing microbiology summary and frequency MIC and disk diffusion data. Note: these analyses will be conducted for the urogenital body site and, if required, pharyngeal and rectal body sites.

- *Neisseria gonorrhoeae* (NG) [Clinical & Laboratory Standards Institute (CLSI) Tables and Listings]
 - Azithromycin-nonsusceptible NG
 - Ciprofloxacin Intermediate NG
 - Ciprofloxacin-resistant NG
 - Extended spectrum cephalosporin (ESC)-nonsusceptible NG
 - Cefixime-nonsusceptible NG
 - Ceftriaxone-nonsusceptible NG
 - Tetracycline-resistant NG
 - β -lactamase positive NG
 - Susceptible to all tested drugs NG
 - Penicillin/Ciprofloxacin and tetracycline -resistant NG
 - Multidrug-resistant (MDR)^a NG
 - Extensively drug-resistant^b (XDR) NG

^aMultidrug-resistant (MDR) NG: [Resistant or nonsusceptible to at least one of the following CFM, AXO or SPT **plus** resistant or non-susceptible to 2 or more of the following antibiotics (CIP, AZM or PEN)]

^bExtensively drug-resistant (XDR) NG: [Resistant or nonsusceptible to two or more of the following antibiotics (CFM, AXO or SPT) plus resistant or non-susceptible to all 3 of the following antibiotics (CIP, AZM or PEN)]- if isolate meets XDR criteria MDR flag is not added.

- *Neisseria gonorrhoeae* (NG) [European Committee on Antimicrobial Susceptibility Testing (EUCAST) Tables and Listings]
 - Azithromycin^a (No NG EUCAST Breakpoints)
 - Ciprofloxacin Intermediate NG
 - Ciprofloxacin-resistant NG
 - Extended spectrum cephalosporin (ESC)-resistant NG
 - Cefixime-resistant NG
 - Ceftriaxone-resistant NG
 - Tetracycline-resistant NG
 - β -lactamase positive NG
 - Susceptible to all tested drugs NG
 - Penicillin^b/Ciprofloxacin and Tetracycline -resistant NG
 - Multidrug-resistant (MDR)^c NG
 - Extensively drug-resistant^d (XDR) NG

^aGiven that there are no EUCAST azithromycin breakpoints for NG, EUCAST has provided guidance for defining azithromycin resistance for the definition of the MDR/XDR category. When applying EUCAST guidelines, a NG isolate with an azithromycin MIC of >1 ug/mL is considered resistant for the sole purpose of determining azithromycin resistance for the MDR/XDR definition. However,

azithromycin interpretations are not reported in any BTZ116577 tables, listings or figures that apply EUCAST guidelines.

^bGiven that there are no EUCAST penicillin breakpoints for NG, EUCAST has provided guidance for defining penicillin resistance for the definition of the MDR/XDR category. When applying EUCAST guidelines, a NG isolate with a penicillin MIC of >1 ug/mL or a positive Beta-lactamase test is considered resistant for the sole purpose of determining penicillin resistance for the MDR/XDR definition. However, penicillin interpretations are not reported in any BTZ116577 tables, listings or figures that apply EUCAST guidelines.

^cMultidrug-resistant (MDR) NG: [Resistant to at least one of the following CIX, CTR or SPE **plus** resistant to 2 or more of the following antibiotics (CIP, AZI or PEN)]

^dExtensively drug-resistant (XDR) NG: [Resistant to two or more of the following antibiotics (CIX, CTR or SPE) plus resistant to all 3 of the following antibiotics (CIP, AZI or PEN)]- if isolate meets XDR criteria MDR flag is not added.

Subcategories for all significant ($n \geq 10$ across treatment groups) drug combinations that comprise MDR/ extensively-drug resistant (XDR) will be analyzed (i.e., tetracycline/ciprofloxacin resistant, penicillin/tetracycline/ciprofloxacin resistant). Note: Some categories may be removed, or new categories added based on final data. Key subcategories with $n < 10$ across treatment groups may be displayed. The Microbiology Team will provide advice on the exact list once data is final and before unblinding.

- The main focus will be ciprofloxacin-resistant, azithromycin-nonsusceptible, ESC-nonsusceptible and MDR NG isolates. These categories will be determined phenotypically based on results from antimicrobial susceptibility testing. Other drug-resistant phenotypes may also be summarized if present in 10 or more participants across treatment groups depending on a final decision from the Microbiology Team. Other drug-resistant phenotypes may include but are not limited to: XDR, ciprofloxacin non-susceptible, or resistance to other drug combinations (i.e., tetracycline/ciprofloxacin, penicillin/tetracycline/ciprofloxacin).
 - A NG isolate will be defined as MDR if it is reported as resistant or nonsusceptible to:
 - At least 1 of the antibiotic classes currently generally recommended for treatment (ESCs [oral and injectable ones are considered separately] and spectinomycin) and
 - ≥ 2 of the of the following: ciprofloxacin, azithromycin or penicillin
 - A NG isolate will be defined as XDR if it is reported as resistant or nonsusceptible to:
 - ≥ 2 of the antibiotic classes currently generally recommended for treatment (ESCs [oral and injectable ones are considered separately] and spectinomycin) and
 - All 3 of the following: ciprofloxacin, azithromycin, or penicillin. (Note: if isolate meets XDR criteria MDR flag is not added.)
- All NG isolates will also undergo genetic characterization to test for the presence of various resistance mechanisms (e.g., quinolone-resistant determining region

mutations). Other drug-resistant genotypes may also be summarized if present depending on a final decision from the Microbiology Team.

- Phenotype and genotype results will appear in summary tables, listings, and figures as subsets in blocks. Note that if a participant has multiple NG isolated at baseline, all isolates may be presented separately if applicable for the summary section. For summaries where a point estimate and confidence interval are presented, analyses will be conducted at the participant-level (i.e., participant with multiple isolates at baseline is counted once).
- GSK microbiologists will give the detailed list of applicable phenotypes and genotypes once microbiology data becomes available.

7.2. Secondary Efficacy Analyses

The secondary clinical questions of interest are: What is the treatment effect on each of the secondary efficacy endpoints after treatment with two doses of gepotidacin 3000 mg, 10-12 hours apart, compared to a single IM 500-mg dose of ceftriaxone plus a single oral 1-g dose of azithromycin in participants with uncomplicated gonorrhea at the body site of interest (rectal/pharyngeal) who have a confirmed NG isolated from baseline culture of their body site (rectal/pharyngeal) specimen. For clarification this population are also required to be ceftriaxone susceptible. Receipt of systemic antimicrobials impacts the endpoint definition. Further details of the estimands for secondary efficacy endpoints are given in Section 2.2. The statistical analyses of all secondary efficacy endpoints will be descriptive in nature, and therefore, will not be subject to multiplicity adjustments.

7.2.1. Endpoint / Variables

- A secondary efficacy endpoint is culture-confirmed bacterial eradication of NG from the rectal body site (i.e., microbiological success) at the TOC visit.
- A secondary efficacy endpoint is culture-confirmed bacterial eradication of NG from the pharyngeal body site (i.e., microbiological success) at the TOC visit.

For definition and derivation, please refer to Section 7.1.1 Endpoint / Variables. The microbiological outcome and response to study treatment (for the rectal and pharyngeal body sites) will be determined for each participant by the same algorithm described in Table 1 Table 2 for the urogenital body site.

7.2.2. Summary Measure

The summary measure for the secondary analyses will be the difference in culture-confirmed bacterial eradication rates for NG between gepotidacin and ceftriaxone plus azithromycin. A similar method to that described in Section 7.1.2 will be used for determining the summary measure for the secondary endpoints, with replacement of urogenital by rectal or pharyngeal, as applicable.

7.2.3. Population of Interest

The secondary population of interest is male and female participants with uncomplicated urogenital and rectal or pharyngeal (depending on the endpoint) gonorrhea caused by *Neisseria gonorrhoeae*. The secondary analyses of the secondary efficacy endpoints will

therefore be performed using the Micro-ITT Rectal Population and the Micro-ITT Pharyngeal Population.

7.2.4. Strategy for Intercurrent Events

For details of the estimand strategy for intercurrent events see Section 2.1 and Section 2.2.1.

7.2.5. Treatment Condition

Gepotidacin 2×3000 mg versus Ceftriaxone 500 mg plus azithromycin 1 g, regardless of adherence.

7.2.6. Statistical Analyses / Methods

7.2.6.1. Statistical Methodology Specification

There will be no multiplicity adjustment for the testing of the secondary endpoints. No formal hypothesis testing will be performed; 95% CIs may be included but only for descriptive purposes. Microbiological response and microbiological outcome for NG from pharyngeal or rectal body sites will be summarized using the Micro-ITT Rectal, Micro-ITT Pharyngeal, ME Rectal and ME Pharyngeal populations for respective body sites. The number and percentage of participants with culture-confirmed bacterial eradication of NG from the rectal body site will be summarized at the TOC visit by treatment group. The corresponding 95% Exact (Clopper-Pearson) CIs will be summarized for each treatment group. The same analysis will also be presented for the pharyngeal body site. The unadjusted difference in microbiological success rate for the two treatments (gepotidacin – ceftriaxone plus azithromycin) will be calculated and summarized along with its 2-sided 95% CI using MN method (adjustment for strata will not be performed).

Participants who do not return for the TOC visit (or have missing data at TOC for any other reason) will be treated as failures. Participants who withdraw from the study prior to TOC will be considered not achieving success for the microbiological response and will be imputed as failures.

7.2.6.2. Subgroup Analyses

Subgroup analysis for rectal or pharyngeal NG body sites will be done for microbiological response at the TOC visit for sex and sexual orientation, age, and ethnicity. Other subgroups (e.g., phenotypic, and genotypic subgroups) defined in Section 5.4.2 will also be analyzed, as appropriate. Continuous data will be summarized using number of subjects, mean, standard deviation, median, minimum and maximum and categorical data will be presented using counts and percentages in subgroup analysis.

Unadjusted difference in microbiological success rate and summarized with 2-sided 95% CI using MN method will be included (adjustment will not be performed). For each specific subgroup, if there are not enough participants (i.e., <10 participants across treatment groups), the corresponding analyses will not be performed.

Analysis/Endpoint Description	Visit	Population	Subgroup
Microbiological Response of Rectal NG	TOC	Micro-ITT Rectal	Sex and Sexual Orientation
	TOC	Micro-ITT Rectal	Age
	TOC	Micro-ITT Rectal	Ethnicity
	TOC	Micro-ITT Rectal	Other subgroup categories defined in Section 5.4.2 & Section 7.1.6.5
	TOC	ME Rectal	Sex and Sexual Orientation
	TOC	ME Rectal	Age
	TOC	ME Rectal	Ethnicity
	TOC	ME Rectal	Other subgroup categories defined in Section 5.4.2 & Section 7.1.6.5
Microbiological Response of Pharyngeal NG	TOC	Micro-ITT Pharyngeal	Sex and Sexual Orientation
	TOC	Micro-ITT Pharyngeal	Age
	TOC	Micro-ITT Pharyngeal	Ethnicity
	TOC	Micro-ITT Pharyngeal	Other subgroup categories defined in Section 5.4.2 & Section 7.1.6.5
	TOC	ME Pharyngeal	Sex and Sexual Orientation
	TOC	ME Pharyngeal	Age
	TOC	ME Pharyngeal	Ethnicity
	TOC	ME Pharyngeal	Other subgroup categories defined in Section 5.4.2 & Section 7.1.6.5

7.3. Exploratory Efficacy Analyses

There will be no multiplicity adjustment for the testing of the exploratory endpoints. No formal hypothesis testing will be performed; 95% CIs may be included but only for descriptive purposes. The details of data displays being presented are in Appendix 9.

7.3.1. Endpoint / Variables/Analysis

7.3.1.1. Gram stain (urogenital only) results at Baseline and TOC visits

- Variables: Gram stain results (WBCs, epithelial cells, and bacteria) from urogenital specimens
- Analysis: The endpoints will be summarized at the Baseline and TOC visits using counts and percentages for ITT Population. A listing of Gram stain results will be provided.

7.3.1.2. In vitro antibacterial susceptibility testing results for NG from urogenital, pharyngeal, or rectal body sites at Baseline, TOC, and FU visits

- Variables: minimum inhibitory concentrations (MICs) and respective interpretations
- Analysis: For antimicrobial susceptibility, results and interpretation from testing for all NG isolates against gepotidacin and other antimicrobials will be summarized by visit, region, country, FDA region, Sex and Sexual Orientation and NG phenotype and genotype subgroups (including phenotypic and genotypic subcategory analysis for subgroups including age, sex and sexual orientation, region, country and FDA region) and antimicrobials tested, for each body site urogenital, rectal and pharyngeal based on respective populations; Micro-ITT, Micro-ITT Rectal, Micro-ITT Pharyngeal, ME, ME Rectal and ME Pharyngeal populations (Note: FDA region only for CLSI summaries). For participants with multiple NG isolates from the same body site at the same visit, unique NG isolate(s) will be selected for analysis as described in Appendix 4 (“keepers data”). For summaries, a participant may be counted multiple times if there are multiple unique NG isolates at baseline for the participant. Percent susceptibility (based on interpretations of susceptible, intermediate, resistant, or nonsusceptible) will be summarized where available. Susceptibility interpretations based on Clinical and Laboratory Standards Institute guidelines (CLSI) and EUCAST will be presented separately.

The overall frequency distribution of minimum inhibitory concentrations (MICs) and the minimum, maximum, 50th percentile (MIC₅₀), and 90th percentile (MIC₉₀) for MIC will be presented. MIC₅₀ and MIC₉₀ refer to the corresponding antimicrobial concentrations required to inhibit 50% and 90% of the isolates obtained, respectively. MIC₅₀ and MIC₉₀ will not be reported if less than 10 isolates are obtained. Details of the MIC₅₀ and MIC₉₀ calculations are presented in Appendix 4. The overall frequency distribution of the disk diffusion zone diameters and the mean, median, standard deviation, minimum and maximum

disk diffusion zone diameters will be presented. The mean, median and standard deviation will not be reported if less than 10 isolates are obtained.

Analyses will be performed to examine the potential relationship between MIC values for the treatment/isolate pairings and microbiological success at the TOC visit. Similar analyses will be performed based on the disk diffusion results. A listing of the susceptibility results as well as a listing of gepotidacin MIC and disk diffusion results including the microbiological outcomes and responses will be provided.

7.3.1.3. Reduction in susceptibility to gepotidacin

- Variables: reduced susceptibility, defined as a post-baseline *N. gonorrhoeae* isolate with a confirmed ≥ 4 -fold increase in MIC result when compared with the baseline MIC of the corresponding *N. gonorrhoeae* isolate from the same participant.
- Analysis: Reduction in susceptibility to gepotidacin will be evaluated by comparing the baseline gepotidacin MIC value based on agar dilution with the value obtained post-baseline. Post-baseline isolates from the same participant and body site with a confirmed ≥ 4 -fold increase in gepotidacin MIC is considered to have developed a reduction in susceptibility to gepotidacin. The relatedness of pre- and post-baseline isolates (e.g., as it relates to 4-fold increases and/or microbiological failures) will be described in a stand-alone report, if needed. The number and percentage of participants who develop reduction in susceptibility to gepotidacin will be summarized by visit and body site for ITT population. Similar development of resistance analysis will be conducted for the study comparators ceftriaxone and azithromycin. Analysis of reduction in susceptibility may be repeated for study treatments by phenotypic and genotypic subgroups (CLSI and EUCAST).

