5.5. Dose Justification

In the Phase II study, both single oral doses of 1500 and 3000 mg gepotidacin were $\geq 95\%$ efficacious (bacterial eradication) against urogenital NG with no unexpected safety signals at either dose. A total of 3 participants failed therapy at the urogenital body site (all with a baseline gepotidacin MIC of 1 $\mu\text{g}/\text{mL}$, which was among the highest MIC for gepotidacin), and analysis of the posttreatment cultures identified 2 isolates that had become resistant to gepotidacin (TOC gepotidacin MICs $\geq 32 \mu\text{g}/\text{mL}$). Further analysis revealed that both isolates also had a pre-existing D86N polymorphism in the topoisomerase IV gene at Baseline. Following treatment, both isolates showed a second mutation, an A92T substitution in the DNA gyrase enzyme, which resulted in reduced susceptibility to gepotidacin. Of the 8 participants in the study with D86N-positive baseline urogenital NG isolates, 5 were microbiological successes (bacterial eradication), including 2 that were infected with baseline organisms with the higher gepotidacin MIC of 1 $\mu\text{g}/\text{mL}$. These data suggest that the 3000-mg single dose may provide close to an effective exposure and that this genotype may be overcome with appropriate dosing.

In the current study, gepotidacin will be administered as 2 oral 3000-mg doses. The two 3000-mg doses, administered 10 to 12 hours apart, compared with the single 3000-mg dose used in the Phase II study, is expected to provide 2-fold higher systemic exposures that allow coverage of NG isolates with higher gepotidacin MIC values, which are likely to be observed in this global Phase III study, and also to reduce the risk of resistance emergence.

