2.3. Study Design

Overview of Study Design and Key Features	
Design Features	
 Phase III, randomized, multicenter, open-label (sponsor-blinded), comparator-controlled, noninferiority study The study duration is approximately 21 days with 3 planned study visits: 
 Baseline (Day 1) Visit TOC (Day 4 to 8) Visit Follow-up (Day 14 to 21) Visit The study will screen and randomize approximately 620 participants to obtain approximately 400 participants with culture-confirmed urogenital gonorrhea in the Micro-ITT Population, for an estimated total of 200 participants per treatment group in the Micro-ITT Population. Enrollment will continue until the target number of participants in the Micro-ITT Population has been reached.
Dosing	
 Participants will receive 1 of the following study treatments: 
 Gepotidacin: 3000 mg administered orally at the study site during the Baseline (Day 1) Visit followed by self-administration of a second oral 3000-mg dose as an outpatient 10 to 12 hours after the first dose. Ceftriaxone plus azithromycin: A single IM 500-mg dose of ceftriaxone plus a single oral 1-g dose of azithromycin administered at the study site during the Baseline (Day 1) Visit.
Time & Events	
 Refer to Appendix 1: Schedule of Activities
Treatment Assignment	
 Participants will be stratified by sex and sexual orientation (men who have sex with men [MSM], men who have sex with women [MSW], or female) and age (<18 years, ≥18 to 65 years, or >65 years). The MSM category will include MSM and bisexual males (i.e., male participants who have sex with both males and females) and participants ≥12 years will be included in the study. Eligible participants will be randomly assigned in a 1:1 ratio to receive 1 of the study treatments (gepotidacin or ceftriaxone plus azithromycin) with dosing as described above.
Interim Analysis	
 No interim analyses are planned for this study.

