4. ANALYSIS POPULATIONS

Population	Definition / Criteria	Analyses Evaluated
Screened Population	
 • All participants who were screened for eligibility. 	
 • Study Population
Intent-to-Treat (ITT) Population	
 • All participants randomly assigned to study treatment. • Participants will be analyzed according to their randomized treatment arm 	
 • Study Population • Efficacy
Microbiological ITT (Micro-ITT) Population	
 • All participants randomly assigned to study treatment who receive at least 1 dose of study treatment and have confirmed NG isolated that is ceftriaxone-susceptible (based on CLSI breakpoints) from baseline culture of their urogenital specimen. • Participants will be analyzed according to their randomized study treatment arm. • This is the primary analysis population. 	
 • Study Population • Efficacy
Microbiological ITT FDA (Micro-ITT FDA) Population	
 • All participants randomly assigned to study treatment who receive at least 1 dose of study treatment and have confirmed NG isolated that is ceftriaxone-susceptible (based on CLSI breakpoints) from baseline culture of their urogenital specimen plus participants who have missing susceptibility and NG isolated at the local laboratory, identified using a recognized method. • Participants will be analyzed according to their randomized study treatment arm. 	
 • Study Population

Population	Definition / Criteria	Analyses Evaluated
Microbiological ITT EU (Micro-ITT EU) Population	
 • All participants who meet the definition of the Micro-ITT population and any participants randomly assigned to study treatment who receive at least 1 dose of study treatment and have confirmed NG isolated that is ceftriaxone-susceptible (based on EUCAST breakpoints) from baseline culture of their urogenital specimen. • Participants will be analyzed according to their randomized study treatment arm. 	
 • Efficacy

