- Susceptibility interpretations will be calculated and reported by the central laboratory and will be based on the CLSI M100 and EUCAST guidelines in effect at that time the bacterial isolate is tested.
- Since CLSI or EUCAST breakpoints for certain drug/bug combinations can change in new yearly editions of the guidelines, as GSK and/or the central laboratory become aware of relevant breakpoint changes, the central laboratory will identify any reports which would qualify as needing a change in interpretation (e.g., a MIC value that was originally reported as susceptible, and would now be considered resistant based on the new breakpoint) and will issue amended reports.
- The final clinical database will report interpretations according to the most recent CLSI M100 and EUCAST interpretations regardless of what the breakpoints were at the time the isolate was initially tested.
- A NG isolate will be defined as MDR if it is reported as resistant (or nonsusceptible for drugs without a resistant breakpoint) to:
 - At least 1 of the antibiotic classes currently generally recommended for treatment (ESCs [oral and injectable ones are considered separately] and spectinomycin) and ≥ 2 of the following: penicillin, ciprofloxacin, or azithromycin
- A NG isolate will be defined as extensively-drug resistant (XDR) if it is reported as resistant) (or nonsusceptible for drugs without a resistant breakpoint) to:
 - ≥ 2 of the antibiotic classes currently generally recommended for treatment (ESCs [oral and injectable ones are considered separately] and spectinomycin) and
 - All 3 of the following: penicillin, ciprofloxacin, and azithromycin (Note: if isolate meets XDR criteria, MDR flag is not added)
- CCI 

Molecular Testing

- All *N. gonorrhoeae* isolates will be submitted to a 3rd party laboratory for whole genome sequencing and screened for mutations in the quinolone-resistance determinant region (QRDR) of *gyrA*, and *gyrB* (encodes for DNA gyrase), and *parC* and *parE* (encodes for topoisomerase IV) genes.
- All isolates will also be subjected to molecular typing by multilocus sequence typing (MLST) and *N. gonorrhoeae* multiantigen sequence typing (NG-MAST) to determine clonality.
- Additional molecular analysis for antibiotic resistance markers will be conducted on a subset of NG isolates based on strain specific susceptibility profiles and may include, but is not limited to:
 - Beta-lactams
 - Penicillinase genes (TEM-1)

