2.31 603	ME, ME Rectal, ME Pharyngeal	EFF_T5	Distribution of Disk Diffusion Results against NG by Drug and Sex and Sexual Orientation (EUCAST)	By body site and sex and sexual orientation By phenotype/genotype within each subgroup (for urogenital site only)	DS, SAC

CONFIDENTIAL

BTZ116577

Efficacy: Tables					
No.	Population	IDSL / Example Shell	Title	Programming Notes	Deliverable
2.31 604	ME, ME Rectal, ME Pharyngeal	EFF_T5	Distribution of Disk Diffusion Results against NG by Drug and Phenotypic/Genotypic Subgroups (EUCAST)	By body site and phenotype/genotype	DS, SAC
2.317.	Intent-to-Treat	EFF_T6	Summary of Reduction in Susceptibility with >= 4-fold Increase in MIC by Drug for Neisseria gonorrhoeae	By body site.	DS, HDL, SAC
2.318.	Micro-ITT, Micro-ITT Rectal, Micro-ITT Pharyngeal	EFF_T7	Summary of Microbiological Success at TOC Visit by MIC Result (CLSI) against NG at Baseline	By MIC result for Gepotidacin, Azithromycin, and Ceftriaxone By phenotypic/genotypic subcategories	DS, SAC
2.319.	ME, ME Rectal, ME Pharyngeal	EFF_T7	Summary of Microbiological Success at TOC Visit by MIC Result (CLSI) against NG at Baseline	By MIC result for Gepotidacin, Azithromycin, and Ceftriaxone	DS, SAC
2.320.	Micro-ITT, Micro-ITT Rectal, Micro-ITT Pharyngeal	EFF_T7	Summary of Microbiological Success at TOC Visit by MIC Result (EUCAST) against NG at Baseline	By MIC result for Gepotidacin, Azithromycin, and Ceftriaxone By phenotypic/genotypic subcategories	DS, SAC
2.321.	ME, ME Rectal, ME Pharyngeal	EFF_T7	Summary of Microbiological Success at TOC Visit by MIC Result (EUCAST) against NG at Baseline	By MIC result for Gepotidacin, Azithromycin, and Ceftriaxone By phenotypic/genotypic subcategories	DS, SAC

Efficacy: Tables					
No.	Population	IDSL / Example Shell	Title	Programming Notes	Deliverable
2.322.	Micro-ITT, Micro-ITT Rectal, Micro-ITT Pharyngeal	EFF_T8	Summary of Microbiological Success at TOC Visit by Disk Diffusion Result against NG at Baseline		DS, SAC
2.323.	ME, ME Rectal, ME Pharyngeal	EFF_T8	Summary of Microbiological Success at TOC Visit by Disk Diffusion Result against NG at Baseline		DS, SAC
2.324.	Micro-ITT, Micro-ITT Rectal, Micro-ITT Pharyngeal	EFF_T8	Summary of Microbiological Success at TOC Visit by Susceptibility Interpretation (based on CLSI MIC) against NG at Baseline		DS, SAC

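### Reduced susceptibility to gepotidacin is reported as a percentage of all randomised participants, although the event needs a baseline isolate at that body site, and strain relatedness is left to a conditional separate report

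*SAP*

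**What the plan says.** **The event.** SAP 7.3.1.3 requires a confirmed MIC rise of at least 4-fold, judged "when compared with the baseline MIC of the corresponding" isolate. The analysis text applies this to "Post-baseline isolates from the same participant and body site with a confirmed" rise in gepotidacin MIC, measured by agar dilution. A similar analysis is planned for ceftriaxone and azithromycin.

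**The population.** "The number and percentage of participants who develop reduction in susceptibility to gepotidacin will be summarized by visit and body site for ITT population". SAP section 4 defines ITT as "All participants randomly assigned to study treatment"; neither an isolate nor a dose is required.

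**The displays.** Table 2.317, "Summary of Reduction in Susceptibility with >= 4-fold Increase in MIC by Drug for" *N. gonorrhoeae*, is an Intent-to-Treat table by body site. It carries the HDL code, which the SAP abbreviation list expands as a headline output. Tables 2.345 and 2.346 repeat the analysis by phenotypic and genotypic subgroup, also on ITT. The neighbouring MIC summaries (7.3.1.2) and beta-lactamase summaries (7.3.1.4) use the site-specific Micro-ITT populations instead.

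**Relatedness.** The sentence just before the one on ITT sends the relatedness of paired isolates, including those with 4-fold increases, to a stand-alone report that is written only if required. Appendix 4 (12.4.2, Keepers Process) mentions a relatedness report for failures without that condition, in a bullet on participants with several baseline isolates. Under Molecular Testing, all isolates are to be sequenced and typed by MLST and NG-MAST.

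**The concern.** The numerator can come only from participants with a baseline isolate and a later isolate at the same site. The stated population includes many who lack the first of these. Pharyngeal and rectal swabs are taken only from willing participants (Protocol 9.1.1). The Follow-up culture is pharyngeal only, and only after positive NAATs at both Baseline and TOC. A percentage of all randomised participants, by visit and site, therefore understates the risk per infected participant.

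The counting rule also cannot separate emergence from acquisition of a different, less susceptible strain. The SAP itself treats MIC differences as evidence about strain identity: in the Keepers Process, same-visit isolates that differ at least 4-fold in three or more antibiotic classes are different strains. Re-infection is limited but not excluded, because condoms are an alternative to abstinence and the requirement ends at TOC.

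This matters because reducing the emergence of resistance is one stated reason for the two-dose regimen (Protocol 5.4 and 5.5). Protocol 5.5 also reports that in Phase II "analysis of the posttreatment cultures identified 2 isolates that had become resistant to gepotidacin", among three urogenital failures.

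**Working it through.** **Inputs**
- SAP 2.3: "The study will screen and randomize approximately 620 participants to obtain approximately 400 participants with culture-confirmed urogenital gonorrhea". Randomisation is 1:1, so 620/2 = 310 ITT and 400/2 = 200 Micro-ITT per arm.
- SAP 8.5.2 uses 310 exposed to gepotidacin.
- Protocol 10.2.1 assumes 90% success in both arms, a margin of -10% and a one-sided level of 0.025.

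**The plan's own figures.** None is given for reduced susceptibility. Two others confirm the denominators.
- Power at 200 per arm: Φ(0.10/√(2 × 0.9 × 0.1/200) − 1.96) = Φ(3.33 − 1.96) = 91.5%; stated, about 91%.
- Chance of seeing an event of 0.75% incidence in 310: 1 − (1 − 0.0075)^310 = 90.3%; stated, 90%.

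**Urogenital site.** Dilution factor = 310/200 = 1.55.

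| Events | Over ITT (310) | Over Micro-ITT (200) |
|---|---|---|
| 1 | 0.32% | 0.50% |
| 2 | 0.65% | 1.00% |
| 4 | 1.29% | 2.00% |

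Micro-ITT is only a stand-in for participants with a baseline isolate. It also drops undosed participants and those whose isolate is not ceftriaxone-susceptible, and the latter can still show a gepotidacin MIC rise. Hence up to about 1.55.

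**Rectal and pharyngeal sites.** The number of baseline positives is not given. *Assumption:* 5% to 30% of an ITT arm, that is 310 × 0.05 = 15.5 to 310 × 0.30 = 93 participants. The factor is then 1/0.05 = 20 down to 1/0.30 = 3.3. One event is 0.32% of ITT against 1/15.5 = 6.5% to 1/93 = 1.1% of site-positives. Protocol 3.1 reports 2 pharyngeal and 3 rectal infections in Phase II, beside 69 evaluable participants.

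**Paired isolates.** At 90% success, 200 × 0.10 = 20 Micro-ITT participants per arm are failures of any kind, including missing TOC. So at most about 20 have a TOC isolate, and two events would be at least 2/20 = 10% of pairs. This answers a different question, because participants whose infection was eradicated were also at risk. It is a reason to show the number of pairs, not to divide by it.

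**Direction of the two effects.** *Assumed example:* four events, 4/310 = 1.29% as planned. If one is an unrelated strain, the related events are 3/200 = 1.5% of Micro-ITT; if two are, 2/200 = 1.0%. The planned figure lies below the first and above the second, so the net error has no fixed sign.

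**The case against.** The strongest reply has five parts.

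1. **The divisor is implied, not written out.** SAP 12.3.2 asks for N, n, frequency and percentage in categorical summaries, and the table shell is not among the documents. The percentage might be taken over participants with data. This stands as a caveat: dilution is the plain reading, not a certainty. A headline table should still state its divisor.

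2. **ITT has a merit.** It keeps participants with ceftriaxone-nonsusceptible baseline isolates, whom Micro-ITT excludes. This stands, and it is why Micro-ITT should not simply replace ITT.

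3. **Strain identity is not ignored.** A reader might infer that any later isolate with a higher MIC counts and that relatedness is never examined. The text does not support that. The rise must be confirmed and measured against the corresponding isolate, in the same participant and body site. A relatedness report is foreseen, and individual cases and genetic results are listed (Listings 609 to 612). What remains is that no typing result enters the count, the SAP does not define the corresponding isolate by typing, and the report is conditional and outside the table.

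4. **Restricting the count to typed matches would bias it.** Events without a typing result would disappear or be relabelled as re-infection, and a match cannot rule out re-infection by the same strain. This stands; all confirmed rises should stay in the total.

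5. **Small numbers, exploratory status.** The count is reported in any case and the analysis is descriptive. This limits the weight of the point, but the percentage will still be read and quoted.

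**Conclusion.** The point holds as a reporting fault in an exploratory but headline analysis. On the plain reading, the urogenital percentage is diluted by up to about 1.55-fold at planned sizes (for two events, 0.65% against 1.0%). It is diluted by more at the optional sites, by an amount the documents do not let one fix; the 3.3- to 20-fold range rests wholly on an assumed positive share. The primary analysis, its power and its type I error are untouched.

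Three stronger readings are tempting and not supported:
- A reader might infer that all of the roughly 220 participants outside Micro-ITT (620 − 400) lack a urogenital isolate. That group also holds undosed participants, those with ceftriaxone-nonsusceptible isolates, and those with a local isolate but missing susceptibility.
- A reader might infer that a corrected denominator would make the rate comparable with Phase II (2/69 = 2.9% of evaluable participants; 2/3 = 67% of urogenital failures). It would not: Phase II gave single doses, and its two isolates were reported at post-treatment MICs of at least 32 µg/mL, not by a 4-fold rule.
- A reader might infer that the reported rate is biased in a known direction. The denominator pulls it down, unrelated strains would push it up, and no re-infection rate is given.

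**What to change.** In SAP 7.3.1.3 and Tables 2.317, 2.345 and 2.346:

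1. Keep the count of all confirmed rises of at least 4-fold.
2. State the divisor. Take the percentage over treated participants with a baseline isolate at that body site and an agar-dilution MIC for the drug concerned, including those with ceftriaxone-nonsusceptible isolates.
3. Show next to it, by arm, visit and site, the number with a paired post-baseline isolate. ITT counts may stay alongside.
4. Split the events into related, unrelated and not typed, using the planned MLST, NG-MAST and sequencing data. Unrelated and untyped events remain in the total.
5. Make the relatedness report unconditional whenever a 4-fold rise occurs, and align 7.3.1.3 with Appendix 4 on this.

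The cost is SAP wording, a denominator flag and a relatedness flag; no new data are needed. The stated percentage becomes less favourable. The relatedness split may have to follow the headline output, because SAP 12.4.2 expects genotype data no sooner than 1 to 2 months after isolate receipt.
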